## **10.2 Secondary study parameter(s)**

### ***Research objective 2: Treatment contacts***

To determine if the number of face-to-face treatment contacts over a period of 37 weeks (i.e. 9 months) is lower in patients who received the 'Aggression' intervention, compared to those who received TAU, a t-test with group as the independent variable and number of received treatment sessions as the dependent variable.

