## SUMMARY

**Rationale:** While internet-based interventions have been used for over ten years in Dutch forensic psychiatric outpatient care, no thorough evaluation study has been conducted yet. Studies on internet-based interventions in other mental healthcare sectors show promising results: they can increase the quality and efficiency of care. However, it is not clear if, why and for whom these interventions work in forensic mental healthcare. It is especially important to study whether these interventions are of added value for this complex patient population, known for its low treatment motivation, co-morbidity and low literacy levels.

**Objective:** The primary objective of this study is to investigate whether the addition of the internet-based intervention 'Aggression' to forensic psychiatric outpatient treatment as usual (TAU) results in better treatment outcomes in terms of self-reported regulatory emotional self-efficacy, treatment readiness, and aggression. Additionally, it is investigated whether the experimental group requires fewer treatment sessions and improves more on dynamic risk factors. Furthermore, to gain more insight into for whom these interventions work, it is investigated whether engagement with the internet-based intervention predicts adherence and effectiveness. Finally, this study aims to explore reasons for the (in)effectiveness of the intervention according to patients and therapists.

**Study design:** To investigate if the use of internet-based interventions is of added value for treatment of forensic psychiatric outpatients, a multicenter, non-blinded, parallel groups, randomized controlled trial design is used. Patients fill out three short self-report questionnaires four times: at baseline, mid-treatment (+6 weeks), post-treatment (+14 weeks) and at follow-up (+26 weeks). Semi-structured interviews with a randomly selected sample of 20 patients from the experimental condition and with all participating therapists are conducted to explain the results of the RCT.

**Study population:** The target group of this study consists of forensic psychiatric outpatients, treated in four Dutch organizations for aggression regulation problems.

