### ***Secondary objectives***

The secondary objectives are:

1. To determine if there is more improvement in improvement regulatory emotional self-efficacy, treatment readiness, and aggression in the experimental than control group during, directly after completing, and three months after completing the internet-based intervention 'Aggression'.
2. To determine if there is more improvement on dynamic risk in the experimental than the control group after completing the internet-based intervention 'Aggression'.
3. To determine if the number of face-to-face treatment contacts over a period of 37 weeks is lower in the experimental than the control group.
4. To determine if the level of engagement with the intervention measured at the beginning, halfway and at the end of the internet-based intervention Aggression, and the adherence to the intervention, is a predictor for effectiveness.
5. To map experiences with the internet-based intervention Aggression of forensic psychiatric patients that followed (part of) the intervention.
6. To map experiences with the internet-based intervention Aggression of therapists that used the intervention in at least five patients.

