Patients will start with the Aggression module after approximately 12 weeks: this might exceed to a maximum of 14 weeks, if the patient for example is not able to start yet or misses several treatment sessions – which happens often in forensic mental healthcare. Participants are assessed four times throughout the study. They are first assessed at

[figure not shown]

baseline (T0), i.e. in week 12. A mid-treatment assessment (T1) is conducted when participants are supposed to be halfway throughout the internet-based intervention, i.e. 6 weeks after baseline, so in week 17. After completing the intervention, post-treatment assessment will be conducted. If participants complete a lesson per week, the intervention should be finished after 11 weeks. However, in practice, this often is not the case, for example because the patient misses treatment sessions or other psychosocial crises can arise that have priority. Consequently, post-treatment assessment will take place 14 weeks after baseline, i.e. in week 25. Finally, a follow-up assessment will be conducted. This assessment will take place 3 months after T2, so during week 37 of the entire study.

At all assessment points, patients will fill out three self-report questionnaires via Qualtrics: Regulatory Emotional Self-efficacy (RESE) scale [31], the Corrections Victoria Treatment Readiness Questionnaire (CVTRQ): a validated self-reported questionnaire [32], and the Dutch version of the Aggression Questionnaire (AVL-AV) [33, 34]. Participants in the experimental condition also fill out the the TWente Engagement with Ehealth and Technologies Scale (TWEETS) [35] at the beginning, halfway and at the end of the internet-based intervention Aggression. Furthermore, the scores of the risk assessment instrument 'Forensisch Ambulante Risico Evaluatie (FARE) [36] - which is part of standard procedures – will be used to assess change in dynamic risk factors in all participants .

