For the second objective, data from risk assessment instruments that are already administered will be collected at baseline and follow-up. Since risk assessment with the FARE has to be performed twice per year, this form of data collection is in line with existing procedures and thus will not take up additional time of patient and therapist. For the third objective, therapists will be asked to indicate the number of treatment sessions that the patient participated in. Therapists can retrieve these data from their calendar, the electronic patient file or supported by the office assistants, the exact method depending on their own preference. Data for the fourth objective on engagement will only be collected from patients in the experimental condition. The TWEETS engagement questionnaire will be built into the internet-based intervention to ensure that it is filled out at the right point in the intervention, i.e. at the beginning, halfway and at the end. Another reason for this is that, if engagement is a predictor for effectiveness, Minddistrict will integrate the TWEETS in all interventions. The fifth and sixth objective will be addressed by means of qualitative data, collected by means of semi-structured interviews with patients and via questionnaires with open-ended with therapists. Finally, at baseline, patients are asked to fill out several questions on demographics, including their gender, age, marital and employment status and education level. Participants will also be asked if they received forensic and/or regular psychiatric treatment in the past. Additionally, at baseline therapists will be asked to provide information

about the inpatient clinic in which the patient is treated, the main treatment goal, type of offense, and diagnoses. These data will be used to describe the sample and will be collected via Qualtrics.

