**Step 4: Baseline assessment (T0) – Week 11**

Before they start with the intervention - thus before they are allocated to a condition - all participants will be sent a link to the self-report questionnaires by the researcher to assess self-efficacy, aggression, treatment readiness and to ask several short questions about sociodemographic variables. These questionnaires will be filled out online via the designated program Qualtrics. The patient is asked to fill out these questionnaires in their own time, but as soon as possible, preferably on the same day. If the patient has not filled out these questionnaire, an automated reminder will be sent after two days. If after that, the patient still did not fill out the questionnaires, the patient is contacted by the researcher via e-mail after five days, to remind them of filling out the questionnaires. If after those two reminders the patient has not completed the questionnaire yet, their therapist is contacted. In the upcoming session, the therapist will the patient for the reason for not completing the questionnaires. If this is due to for example difficulties with answering the questions, the researcher will contact the patient and fill the questionnaires out together. If the patient indicates that they do not want to fill out the questionnaire due to any other reason, the therapist will discuss if participation in the study is still an option.

Besides the self-report questionnaires, the risk assessment instrument FARE will be administered by the therapist as part of standard treatment. As mentioned before, because the FARE is embedded in standardized structures of the organization, it might be that this risk assessment instrument is administered several weeks before the questionnaires.

In this week, the therapist will also receive a short questionnaire via Qualtrics about background information regarding the patient (inpatient clinic in which the patient is treated, the main treatment goal, type of offense, and diagnoses).

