**Step 5: Randomization and start intervention – Week 12**

Directly after the patient has provided informed consent, the patient is randomized by the researcher. This is communicated to the therapist, who will let the patient know whether they will start with the intervention 'Aggression' or if they will participate in the control group.

After the first session of the internet-based intervention is finished, the TWEETS will be administered to participants in the experimental group via the Minddistrict platform, because the TWEETS is integrated in the intervention.

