### ***Step 9: Follow-up assessment (T3) – week 37***

37 weeks after start of treatment, the three questionnaires (self-efficacy, aggression and treatment readiness) will be again administered via Qualtrics. If, at this point, the patient is not being treated at the outpatient clinic anymore, he or she will be contacted by the researchers. This will be clearly communicated in the informed consent form and by the therapist. The FARE that will be administered about 6 months after treatment as part of standard assessment by clinics will be used for the follow-up assessment. Participants will receive the second €10 voucher after completing the this final assessment.

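### The 37-week count of treatment contacts has no stated start; by the schedule it apparently includes 8 to 12 weeks before randomisation, which the unadjusted t-test leaves in as noise

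*Combined protocol and SAP*

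**What the plan says.** The third secondary objective in section 2 reads "To determine if the number of face-to-face treatment contacts over a period of 37 weeks is lower in the experimental than the control group". Section 10.2, where this outcome is numbered research objective 2, repeats the aim: "To determine if the number of face-to-face treatment contacts over a period of 37 weeks (i.e. 9 months) is lower in patients" who received the module. The planned test is a t-test with group as the only explanatory variable and the session count as outcome. Neither place gives a start or an end for the window.

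On data collection, section 8.1 says that "therapists will be asked to indicate the number of treatment sessions that the patient participated in". The source may be the therapist's calendar, the patient file or the office staff, as the therapist prefers. No dates are given.

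The schedule gives these anchors:
- Summary: assessments are "at baseline, mid-treatment (+6 weeks), post-treatment (+14 weeks) and at follow-up (+26 weeks").
- Section 3.3, on T3: "This assessment will take place 3 months after T2, so during week 37 of the entire study".
- Section 8.3, Step 4: "Baseline assessment (T0) – Week 11".
- Section 8.3, Step 5: "Randomization and start intervention – Week 12".
- Section 8.3, Step 9: "37 weeks after start of treatment, the three questionnaires (self-efficacy, aggression and treatment readiness) will be again administered".

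Two passages blur the date of randomisation. The text of Step 5 has it follow immediately on consent, and Step 3 places consent in weeks 8 to 11. Section 3.3 puts baseline in week 12, not week 11.

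**The concern.** A contact count needs a start date. Without one, therapists in four organisations may count from different points, and the result cannot be reproduced.

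If the count starts at treatment start, part of it was fixed before the patient had an allocation. Those contacts cannot differ between arms because of the module. They add between-patient variation to the outcome, and a t-test on the raw total does nothing to remove it. At stake is the precision of the comparison that tests whether the module saves sessions, which the Summary names as an aim. The primary outcomes are not involved.

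**Working it through.** **1. Which 37 weeks?** With baseline in week 11, the Summary's offsets give 11 + 6 = 17 (T1), 11 + 14 = 25 (T2) and 11 + 26 = 37 (T3). These match the week numbers in section 8.3. A baseline in week 12 would give 18, 26 and 38, which do not. So week 37 is counted from treatment start.

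Counting 37 weeks from baseline or randomisation would end in week 11 + 37 = 48 or 12 + 37 = 49, well past T3. The timeline under section 8.4 has inclusion to February 2023 and the last follow-up by September 2023. From 28 February 2023, 26 weeks ends on 29 August, which fits; 37 weeks ends on 14 November, which does not. Session counts could be retrieved later, so this supports the treatment-start reading without proving it.

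**2. Share before randomisation.** By the step headings: 11/37 = 29.7% and 12/37 = 32.4%. If randomisation follows consent at once and consent is in week 8: 8/37 = 21.6%.

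**3. The plan's own power figure.** Section 4.4 uses a difference of 0.5 SD, power 0.80 and a two-sided 5% t-test. The exact calculation gives 63.8, so 64 per arm, as stated. This figure is for the primary outcomes. No power is stated for contacts.

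**4. Effect on precision.** Let v be the pre-randomisation variance divided by the post-randomisation variance, and r the correlation between the two counts. Then

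SD(total)/SD(post) = sqrt(1 + v + 2r·sqrt(v)).

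An effect of d post-randomisation SDs becomes d divided by this ratio on the total, and d/sqrt(1 − r²) after adjustment for the pre-randomisation count.

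Assumptions, none given in the documents for contacts: d = 0.5 and r from 0 to 0.5. Two values of v are shown: 0.04, and variance in proportion to weeks (12/25 = 0.48). The number per arm is either 154 × 0.8 / 2 = 61.6 (20% lost) or 154 / 2 = 77 (none lost). Power is from the noncentral t, two-sided 5%:

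| Outcome analysed | 61.6 per arm, r = 0 / 0.5 | 77 per arm, r = 0 / 0.5 |
|---|---|---|
| Post-randomisation contacts, unadjusted | 0.786 | 0.869 |
| Post-randomisation contacts, adjusted | 0.786 / 0.889 | 0.869 / 0.945 |
| 37-week total, v = 0.04 | 0.770 / 0.696 | 0.856 / 0.791 |
| 37-week total, v = 0.48 | 0.619 / 0.463 | 0.717 / 0.552 |

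For example, v = 0.48 and r = 0 gives a ratio of sqrt(1.48) = 1.217, so d = 0.5/1.217 = 0.411.

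With d = 0.2 and 61.6 per arm, power is 0.196 on post-randomisation contacts and 0.116 to 0.191 on the total across the same cases.

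**5. Can the raw total be the better choice?** Against unadjusted post-randomisation contacts, yes, if r is below −sqrt(v)/2, which is −0.10 for v = 0.04 and −0.35 for v = 0.48. Against the adjusted analysis, in units of post-randomisation variance,

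(1 + v + 2r·sqrt(v)) − (1 − r²) = (sqrt(v) + r)² ≥ 0.

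So adjustment is never less precise, apart from one degree of freedom, when all patients share the same pre-randomisation interval. With intervals that vary, this is expected but not proved.

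**The case against.** The start is strongly implied: only one 37-week span exists, and a single clause would make it explicit. What then remains is a more efficient analysis, and an unadjusted t-test in a randomised trial is valid. Both points stand and keep the severity low. They do not remove the gap in section 8.1, where therapists still have no window.

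The larger power losses are also the least supported. Section 5.1.2 plans weekly sessions and patients are still in treatment at randomisation, which limits the spread beforehand. Step 9 foresees some patients having left treatment by T3, which adds variance only afterwards. Both favour a small v, where the loss can be as little as 0.786 against 0.770. An effect of 0.5 SD is doubtful as well: the Summary says that the module replaces no part of treatment. This stands, so the figures are an illustration and not an estimate.

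The 20% loss in section 4.4 is defined by questionnaires, whereas contacts come from therapists and section 10.1 specifies intention to treat. That stands too, and is why 77 per arm is shown beside 61.6.

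A reader might infer that the pre-randomisation weeks bias the comparison. The documents do not support that. Those contacts precede allocation, so they have the same expectation in both arms and cancel from the difference in means.

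**Conclusion.** The point holds as a minor one. The window has no stated start, and the schedule implies one that begins 8 to 12 weeks before randomisation (22 to 32% of the 37 weeks). The planned test does not adjust for that period. The start is inferred from the schedule and is not written for this outcome, so the word apparently must stay.

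The expected consequence is lost precision on one secondary outcome. Its size is not derivable. Under the assumptions above it runs from a power loss of about 2 percentage points (v = 0.04, r = 0, 61.6 per arm) to about 32 (v = 0.48, r = 0.5). A clearly negative correlation would reverse the loss for the raw total, but nothing in the documents suggests one. With an effect near 0.2 SD, the test has little power under either definition.

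It would be tempting to say that the trial misses its planned power here. It does not, because the plan sets none for contacts.

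**What to change.** In sections 2 and 10.2, define the outcome as face-to-face contacts in one fixed period from each patient's randomisation date. A period of 25 weeks, for example, ends at about T3 (12 + 25 = 37) without depending on the date of that assessment. Give therapists the same window in section 8.1.

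Replace the t-test with a linear regression of this count on group, with pre-randomisation contacts as covariate. Express the covariate as contacts per week from treatment start to randomisation, because that interval differs between patients. Report total contacts from treatment start descriptively.

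The cost is a few sentences in three sections. Therapists must also split the session counts that they already retrieve at a known date.

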### ***Research objective 3: Dynamic risk factors***

To determine if there is more improvement on dynamic risk factors as measured by a risk assessment instrument in patients who received the internet-based intervention 'Aggression' as an addition to TAU, compared to those who only receive TAU. For this research objectives, the same analysis as for research objective 1 will be used.

### ***Research objective 4: Engagement***

To investigate whether engagement predicts effectiveness, simple linear regression analyses will be run for three variables: regulatory emotional self-efficacy, treatment readiness, and aggression. The score on the TWEETS on T0, T1 and T2 will be used as independent variables in three different regression analyses. The change scores (i.e. difference between scores on T2 and T0, and the difference between scores on T3 and T0) for all relevant variables (self-efficacy, treatment readiness and aggression) will be used as dependent variables for two regression analyses. These scores will be added in a second analysis to

measure whether it adds predictive value on the dependent variables. Furthermore, in order to investigate if the TWEETS scores predict adherence, three analyses with the TWEETS score on T0 and T1 as dependent variables are run, this time with the number of finished lessons of the intervention as dependent variable.

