### ***Engagement – TWEETS***

Many studies have been conducted to identify why and for whom specific internet-based interventions work. Up until now, the use of sociodemographic factors as predictors has not provided answers to these questions. Engagement is a non-specific factor that can be used to predict effectiveness of and adherence to internet-based interventions [46]. Engagement refers to the extent to which someone is involved or occupied with something, and is often related to a positive outcome, such as effectiveness. In the context of digital behaviour change interventions, engagement contains an affective, behavioural and cognitive component [46]. The affective component is focused on positive or negative feelings towards the intervention and the way in which the intervention fits with a person's identity: do people identify with the design of the technology and what it stands for? Behavioural engagement is focused on the routine that a user has regarding the use of an intervention and the extent to which it requires effort and is part of one's daily life. The cognitive component of engagement refers to the extent to which an intervention supports the user in reaching their goals and is seen as useful for their behaviour change.

In this study, engagement is measured with the TWente Engagement with Ehealth and Technologies Scale (TWEETS). The scale employs a definition of engagement that incorporates behaviour, cognition, and affect, and has been shown to have a good validity and reliability [35]. The TWEETS contains only 9 items – with three items per component of engagement - and has three slightly different versions: one for expected engagement, to be used when someone starts using an intervention, one for current engagement, to be used

during the use of an intervention, and one for past engagement, to be used when a user has completed or stopped using an intervention.

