### 8.1.3 Other study parameters

To describe the characteristics of the sample, information about treatment objectives, diagnoses, age, gender, and the inpatient clinic in which they are treated will be used. These data will be retrieved at T0 from the therapist by means of a Qualtrics questionnaire. In this way, the researchers do not need access to the personal patient file.

Table 1: Overview of study parameters

Variable	Instrument	Assessment point	Invested time
Regulatory emotional self-efficacy	Regulatory Emotional Self-efficacy (RESE) scale [31]	T0, T1, T2, T3	5 min. per assessment point, 20 minutes in total
Treatment readiness	Corrections Victoria Treatment Readiness Questionnaire (CVTRQ) [32]	T0, T1, T2, T3	5 min. per assessment point, 20 minutes in total
Aggression	Aggression Questionnaire [17, 18].	T0, T1, T2, T3	5 min. per assessment point, 20 minutes in total
Risk assessment	Forensisch Ambulante Risico Evaluatie (FARE) [36]	T0 & T3*	N.a. – part of standard procedures
Engagement	TWente Engagement with Ehealth and Technologies Scale (TWEETS) [35]	T0, T1 & T2 (only in the experimental group)	5 min. per assessment point, 15 min. in total (only for experimental group)
Patients' perceived effectiveness and points of improvement	Semi-structured interviews	T2	Ca. 30 min
Therapists' perceived effectiveness and	Open-ended questionnaires (Qualtrics)	T2	Ca. 15 min

points of improvement			
-----------------------	--	--	--

*\* In this study, the FARE that is administered during the standard treatment trajectory are used to not interfere with standard procedures, meaning that the exact date of FARE administration can slightly differ from the T0 and T3 assessments.*

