### ***Step 7: Assessment post-intervention (T2) – Week 25***

After 15 weeks, the three questionnaires on self-efficacy, aggression and treatment readiness will be administered again, following the same procedures as described before. Furthermore, after finishing the final lesson of the intervention, the patient will fill out the TWEETS on the Minddistrict platform.

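### Twelve of the 18 engagement regressions use a halfway or end TWEETS score to predict change that has already partly or wholly occurred when the score is taken

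*Combined protocol and SAP*

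**What the plan says.** The secondary objectives (section 2) ask whether engagement is a predictor of effectiveness: "To determine if the level of engagement with the intervention measured at the beginning, halfway and at the end of the internet-based intervention Aggression". Section 10.2 turns this into regressions: "To investigate whether engagement predicts effectiveness, simple linear regression analyses will be run for three variables". On the predictors it says: "The score on the TWEETS on T0, T1 and T2 will be used as independent variables in three different regression analyses". The dependent variables are "The change scores (i.e. difference between scores on T2 and T0, and the difference between scores on T3 and T0", for each of the three questionnaires.

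Section 8.3 fixes when TWEETS is taken. First score: "After the first session of the internet-based intervention is finished, the TWEETS will be administered" (Step 5). The second goes with the mid-treatment assessment (Step 6), and section 8.1 says TWEETS is built into the module and appears halfway through it. Third: "after finishing the final lesson of the intervention, the patient will fill out the TWEETS on the Minddistrict platform" (Step 7). Table 1 nevertheless lists the scores as "T0, T1 & T2 (only in the experimental group".

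Section 8.1.2 describes what the scale covers, including: "The cognitive component of engagement refers to the extent to which an intervention supports the user in reaching their goals". Section 8.1 adds that if engagement proves to be a predictor of effectiveness, the platform developer will build TWEETS into all its interventions.

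**The concern.** A predictor should be measured before the outcome it predicts. Both change scores start at T0, before allocation, while the halfway and end TWEETS are taken well inside the change window or at its end. A patient who has already improved has a reason to rate the module as helpful. The regression then shows a positive slope even if engagement has no bearing on what follows.

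Nothing in section 10.2 limits the outcome to change after the TWEETS, adjusts for change already made, or labels these pairings as association only. The second analysis mentioned there does not say clearly which scores are added and does not mention prior change.

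At stake is the reading of objective 4. The introduction presents engagement as a way to learn why the module works for particular patients, and section 8.1 ties a rollout decision to the answer.

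**Working it through.** **1. The plan's own figures.** The documents give no figure for these regressions. The sample size does reproduce: a two-sided t-test with d = 0.5, alpha 0.05 and power 0.80 needs 63.8, so 64 per arm and 128 in total; 128 × 1.2 = 153.6, so 154 (section 4.4). With 1:1 allocation (assumed), 154/2 = 77 patients can have TWEETS scores. After 20% dropout, 77 × 0.8 = 61.6, about 62.

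**2. Share of the change window already elapsed.** The Summary puts T1, T2 and T3 at 6, 14 and 26 weeks after baseline. Section 3.3 expects the module to finish after 11 weeks at one lesson per week and says this often does not happen. I take the end TWEETS as falling between week 10 and week 14.

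| TWEETS | T2−T0 | T3−T0 |
|---|---|---|
| After lesson 1 | near the start | near the start |
| Halfway (week 6) | 6/14 = 43% | 6/26 = 23% |
| End, on schedule (week 10–11) | 10/14 to 11/14 = 71–79% | 10/26 to 11/26 = 38–42% |
| End, at T2 (week 14) | 14/14 = 100% | 14/26 = 54% |

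**3. Count.** 3 TWEETS times × 2 change scores × 3 outcomes = 18 regressions. The halfway and end scores account for 2 × 2 × 3 = 12, the first score for 1 × 2 × 3 = 6.

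**4. Illustration with no forward effect.** Assumptions, none from the documents:
- TWEETS correlates ρ with true change so far and is unrelated to later change.
- True change is a random walk with SD 0.8 of the baseline SD by week 26, so its variance per week is v = 0.64/26 = 0.0246.
- Questionnaire reliability is 1.0 or 0.85. At 0.85 the error variance is 0.15/0.85 = 0.176 per score, or 0.353 for a difference of two scores.
- There are 40 scores (assumed module completers) or 62.
- The end score is taken at week 14.

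The correlation that the planned regression sees is r = ρ × √[v × weeks to TWEETS / (v × weeks to outcome + error variance)]. The chance of p < 0.05 is about Φ(atanh(r) × √(n−3) − 1.96). For ρ = 0.3 and the T2−T0 change:
- End, reliability 1.0, n = 62: r = 0.300; 0.3095 × 7.68 − 1.96 = 0.42; 66%.
- End, reliability 0.85, n = 40: r = 0.3 × √(0.345/0.698) = 0.211; 0.214 × 6.08 − 1.96 = −0.66; 26%.
- Halfway, reliability 1.0, n = 62: r = 0.3 × √(6/14) = 0.196; 0.199 × 7.68 − 1.96 = −0.43; 33%.
- Halfway, reliability 0.85, n = 40: r = 0.3 × √(0.148/0.698) = 0.138; 0.139 × 6.08 − 1.96 = −1.11; 13%.

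Simulation (4,000 runs per cell, ρ = 0.3) agrees:

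| Pairing | n = 40, rel. 0.85 | n = 62, rel. 0.85 | n = 62, rel. 1.0 |
|---|---|---|---|
| Halfway with T2−T0 | 13% | 18% | 33% |
| Halfway with T3−T0 | 10% | 15% | 19% |
| End with T2−T0 | 26% | 38% | 67% |
| End with T3−T0 | 18% | 29% | 40% |

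At ρ = 0 every rate is about 5%. At ρ = 0.5, n = 62 and reliability 0.85, the range over the four pairings is 34–82%.

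If the end score is taken on schedule at week 10, the end/T2−T0 range falls. For reliability 1.0 and n = 62, r = 0.3 × √(10/14) = 0.254 gives 51%. For reliability 0.85 and n = 40, r = 0.3 × √(0.246/0.698) = 0.178 gives 19%.

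**5. Time-ordered models, same assumptions, n = 62.** The halfway score is tested against T2 or T3 outcome adjusted for T0 and T1 scores, and the end score against T3 outcome adjusted for T0, T1 and T2 scores. False positives are about 5% with error-free scores. At reliability 0.85 they are 7–8% (ρ = 0.3) and 9–14% (ρ = 0.5), against 15–38% and 34–82% as planned.

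**The case against.** Several points on the other side stand.

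- The six regressions on the first TWEETS follow only one lesson and can test prediction as planned. A reader might infer that objective 4 cannot be answered at all; the documents do not support that.
- A reader might also infer that the end score always comes after the whole T2−T0 change. On schedule, 3–4 of the 14 weeks still lie ahead, and for T3−T0, 12 of the 26 weeks follow T2.
- The simulated rates are in effect the power of a correlation test at a correlation that was put in. No correlation, reliability or number of completed TWEETS comes from the documents. The rates show direction and rough size and are not an expected error rate.
- The goal-support content is one of three TWEETS components, 3 of 9 items, and the item wording is not given. That the end score uses the past-engagement version is a reasonable inference, but section 8.3 does not state it.
- The T0 label is a small matter, because section 8.3 makes the actual timing clear.

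The plan also says predictor and not cause. That does not remove the problem: prediction without any causal claim still needs the predictor to precede the outcome, and the stated aim and the rollout decision give the result a direction.

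**Conclusion.** The point holds for the 12 regressions that use the halfway or end TWEETS. Part of the change they are meant to predict has already occurred when the score is taken: 43% or 23% of the window for the halfway score, and about 71–100% or 38–54% for the end score. These shares rest only on the stated weeks. They measure elapsed time and equal the share of change only if change is even over time.

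Whether earlier improvement actually raises TWEETS in these patients is unknown. The documents make it plausible but do not show it. If it does, the planned analysis cannot tell it from engagement predicting effect, and the false-positive rate could be several times the nominal 5%.

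A reader might infer that the trial's conclusion on effectiveness is at risk. It is not: TWEETS is collected only in the experimental arm, for a secondary objective, and neither the randomised comparison nor the effectiveness rules in section 10.1 use it. The change is worth making before analysis, mainly because of the decision attached to the result.

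**What to change.** In section 10.2, objective 4:
- Keep the first TWEETS as the main predictor of T2 and T3 outcome.
- Use the halfway TWEETS only for T2 and T3 outcome, adjusted for T0 and T1 scores, among patients who completed it by about the T1 assessment. Because it is triggered by module position, a slow patient may complete it later.
- Use the end TWEETS only for T3 outcome, adjusted for T0, T1 and T2 scores, among patients who completed it by T2.
- Report the end TWEETS with T2−T0, and any other pairing out of time order, as association only.
- Record the TWEETS completion date so that the order can be checked; the documents do not say that it is recorded.
- In Table 1 and section 10.2, label the first TWEETS 'after lesson 1' instead of T0.

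Cost: the questionnaire scores needed are already planned, so this is mostly rewording, plus the completion date if it is not already kept. Four of the six regressions per outcome are re-specified or relabelled, and some patients leave the time-ordered analyses. With measurement error the adjusted models still exceed 5% somewhat (7–14% in the settings above), so a weak positive finding from the halfway or end score should be read with caution.
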